#### 2.1.2 Exploratory Registry Arm

Subjects enrolled that were treated for a failed surgical bioprosthetic aortic valve true inner diameter size of < 19 mm or > 27 mm will be included in a separate exploratory analysis.

### 2.2 Statistical Methods

#### 2.2.1 Descriptive Statistics for Continuous Variables

For continuous variables (e.g., age, BMI, heart rate, etc.), results will be summarized with the numbers of observations, means, and standard deviations, with quartiles, minimums, maximums, and 95% confidence intervals for the means, when specified.

#### 2.2.2 Descriptive Statistics for Categorical Variables

For categorical variables (e.g. gender, diabetic status, etc.), results will be summarized with subject counts and percentages/rates, with exact 95% Clopper-Pearson confidence intervals, when specified.

#### 2.2.3 Survival Analyses

Survival analysis will be conducted to analyze time-to-event variables. Subjects without events will be censored at the time of analysis. Survival curves will be constructed using Kaplan-Meier estimates and Greenwood standard errors.

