### 2.1 Background and Justification for Study

Increased use of bioprosthetic valves, combined with increased life expectancy, is resulting in the need for treatment options for patients with failing bioprosthetic valves. Operative mortality for redo aortic valve surgery is generally low (2% to 7%) in suitable candidates. However, mortality risk can increase to more than 30% in high-surgical risk patients. Implantation of a transcatheter aortic valve in a failed surgical aortic bioprosthesis to achieve adequate valvular function for symptom relief represents a minimally invasive alternative to conventional redo surgery.

The most common reasons for surgical bioprosthetic aortic valve replacement, or ViV treatment, is structural valve deterioration caused by 1) wear and tear, 2) calcific degeneration, 3) pannus, 4) endocarditis, and 5) thrombus.

Two types of commercially available transcatheter heart valves (THVs) are currently approved for ViV in Europe and the United States: the balloon expandable Edwards Sapien XT and Sapien 3 THVs (Edwards Lifesciences, Irvine, CA) and the self-expanding Medtronic CoreValve, Evolut R, and Evolut Pro THV (Medtronic, Dublin, Ireland).

Medtronic's CoreValve was the first to obtain CE Mark and FDA approval in 2014 and 2015 respectively for ViV with data from the Global ViV registry used to support the expanded indication. The Global Valve-in-Valve Registry was initiated in December 2010 and designed to collect retrospective and prospective data from centers worldwide that had ViV experience with either CoreValve or Edwards Sapien devices, used off-label at that time. A total of 202 patients with degenerated bioprosthetic valves from 38 centers across Europe, North America, Australia, New Zealand and the Middle East contributed data to the registry. Of these 202 patients (mean age  $77.7 \pm 10.4$  years; 52.5% men, 42% with stenosis as primary mode of failure), 124 underwent Valve-in-Valve with a CoreValve THV and 78 with an Edwards SAPIEN THV. At 30 days, 185 patients had survived, 17 patients died (8.4%). There were no differences between the CoreValve and Edwards SAPIEN patients with respect to mortality, major vascular complication, stroke, or need for a permanent pacemaker. At 30 days, mortality and stroke rate (8.4% and 2%, respectively) are comparable to the rates in other transcatheter aortic valve replacement cohorts. At 1 year, freedom from all-cause mortality was 85.8%.

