## 6.3 Informed Consent

Patients that have had a failed surgical aortic bioprosthetic valve and underwent a Portico ViV Implant procedure may be identified and screened as potential study subjects. Patients may be identified from their study site's procedure records for potential study enrollment. Once identified, each patient must complete the informed consent process prior to study participation.

The Principal Investigator or his/her authorized designee will conduct the Informed Consent process, as required by applicable regulations and the center's local Ethics Committee (EC). This process will include a verbal discussion with the patient on all aspects of the study which are relevant to the patient's decision to participate, such as details of data being collected, any potential benefits and potential risks of participation. During the discussion, the Principal Investigator or his/her authorized designee will avoid any improper influence on the patient and will respect the patient's legal rights. The patient must be provided with the Informed Consent Form (ICF) written in a language that is understandable to the subject and has been approved by the center's local EC. The patient must have adequate time to review, ask questions and consider participation.

If the patient agrees to participate and signs the ICF, the ICF must be signed and dated by the subject and by the person who obtained the subject's consent. The signed original form will be filed in the subject's hospital or research charts, and a copy will be provided to the subject by the Investigator or his/her authorized designee.

The Principal Investigator or his/her authorized designee will document the informed consent process in the subject's hospital/clinic and/or research charts. The date of signature will be entered on an applicable Case Report Form (CRF).

Failure to obtain the ICF from a subject prior to study enrollment should be reported to the Sponsor within 5 working days and to the study site's EC according to their reporting requirements.

If, during the study, new information becomes available that can significantly affect a subject's future health and medical care, the Principal Investigator or his/her authorized designee will

provide this information to the subject. If relevant, the subject will be asked to confirm their continuing informed consent in writing.

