## 8.2 Subject Lost to Follow-up and Withdrawal

Subjects must be informed about their right to withdraw from the study at any time and for any reason without sanction, penalty or loss of benefits to which the subject is otherwise entitled. Withdrawal from the study will not jeopardize the subject's future medical care or relationship with the study site Principal Investigator. Subjects will be requested to provide the reason for the request to withdraw from the study. The Principal Investigator must make all reasonable efforts to retain the subject in the study until completion of the study.

A study subject that has been withdrawn from the study will not be replaced. All data collected up to the point of their study withdrawal will be reported and included in the data analysis as applicable.

If a subject cannot be reached and review of their medical records does not provide sufficient information to assess the status and performance of their VIV, the site should make every effort to reach the subject and their local or referring physician. The efforts undertaken to contact the subject, referring physicians, including internists as well as cardiologists, family members, or other alternate contacts must be noted in the subject's records. These efforts must include at least two attempts of telephone contact on separate dates, and a registered letter before considering the subject lost-to-follow-up.

Reasons for early termination include, but are not limited to:

1. Subject refuses to continue participating in the study, withdraws consent
2. Subject is 'lost to follow-up': Site personnel should at all times make all reasonable efforts to locate and communicate with the subject in order to achieve subject compliance to the scheduled follow-up visits:
  - A subject will be considered 'lost to follow-up' after one missed visit, and a minimum of two phone calls from the investigational site to the subject or listed contact of the subject. These two phone calls need to be documented in the subject's hospital records.
  - If these two attempted phone calls are unsuccessful, a letter should be sent to the subject's last known address or general practitioner and a copy of this letter should be maintained in the subject's hospital records.

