Note: If a subject missed one or more of the scheduled follow-up visits (inclusive of the assigned visit windows), this will be considered as a missed visit. The subject may therefore still return for subsequent follow-up visits and will not be withdrawn from the study.

If a subject withdraws from the clinical study, the site will record the subject's reasons for withdrawal, on a Withdrawal CRF.

The status of the subject's condition should be documented at the time of withdrawal on any ongoing adverse event forms.

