## 9 DATA COLLECTION AND EVALUATION OF ENDPOINTS

The Principal Investigator is responsible for ensuring all study data is collected as required per the protocol scheduled time points. In addition to accessing the subject's medical records, data collection may also occur remotely by phone contact, mail, in-person, or through email. The clinical study will be conducted in accordance with the protocol. All parties participating in the conduct of the study will be qualified by education, training and/or experience to perform their tasks. This training will be documented appropriately. The data collection elements required for each follow-up are listed below and in **Table 3** below.

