#### **9.4 Subject Study Completion**

Subject participation in the study will conclude when:

1. The subject completes the 5-year data collection time point.
2. When consent is withdrawn (by the subject or legal authorized representative).
3. When the subject is deceased at the time of enrollment or dies during the study, their study completion will occur after their last study follow-up was available, including details of what led up to death and the cause of death.
4. When the subject is lost to follow-up, their study completion will occur after their last study follow-up.
5. For subject's where the Portico delivery system entered their body but was not successfully implanted, they will complete the study after 30 days from the attempted procedure.

Upon completion of subject participation in this data-collection study, the subject will continue to receive follow-up as per standard of care.

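### SAP 2.2.3 censors event-free subjects at the analysis date, so a subject treated more than a year before lock whose record stops early counts as event-free to 1 year in the co-primary Kaplan-Meier rate

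*SAP*

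**What the plan says.** SAP 2.2.3, which governs all time-to-event analyses, states: "Subjects without events will be censored at the time of analysis". SAP 2.3.1.2 applies Kaplan-Meier with Greenwood standard errors to the co-primary performance endpoint, death from any cause or disabling stroke at 1 year. It adds one exception: follow-up is censored at a first COVID-19-related event. Nothing is said there about loss, withdrawal or study exit.

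Other sections show that observation can stop before 1 year:

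- SAP 2.6 allows for withdrawals, losses and missed 1-year visits when the data are locked.
- SAP 2.1.1 admits any subject in whom the delivery system entered the vasculature. Protocol 9.4 says of subjects without a successful implant that "they will complete the study after 30 days from the attempted procedure", and Protocol 11.6.1 gives the same 30-day limit.

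Some text points towards ordinary censoring. Protocol 8.2 says of withdrawn subjects: "All data collected up to the point of their study withdrawal will be reported and included in the data analysis as applicable". SAP 2.8 bases analyses on available data and plans no imputation. Neither names a censoring date.

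**The concern.** Kaplan-Meier is used so that a subject leaves the risk set when observation ends. If an event-free subject last documented at day 40 is instead censored at a lock date beyond day 365, the analysis credits that subject with about 11 event-free months that nobody observed. Risk sets are then too large, each event removes too small a fraction of them, and the standard error treats the year as fully observed.

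For a given set of observed events, the error runs in one direction: a lower event rate and a smaller standard error. The rate is one of two co-primary results. SAP 2.10 prespecifies no hypothesis test for either, so the estimate and its precision are the whole result.

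**Working it through.** **Inputs.** The documents give no expected 1-year rate, loss rate or failed-implant rate, so there is no planned figure to reproduce.

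- N = 100, the maximum in SAP 1.3.
- Proxy event curve from the valve-in-valve registry described in Protocol 2.1: 17 of 202 dead at 30 days (8.4%), and 85.8% free of death at 1 year, so F(30 d) = 8.4% and F(1 y) = 14.2%. This covers deaths only, not stroke.
- Loss or exit fraction L = 5, 10 or 20%: an assumption, taken as non-informative.

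**Step 1: what the rule does.** Suppose every procedure is more than 1 year before lock, and leave the COVID-19 exception aside. Nobody then leaves the risk set before day 365 except by an event. With D events, the Kaplan-Meier product telescopes to (N − D)/N, so the estimated rate is D/N. The Greenwood sum telescopes to 1/(N − D) − 1/N, which gives SE = sqrt(p(1 − p)/N) with p = D/N. Censoring at last known status makes every risk set the same size or smaller, so on the same events it gives a rate that is equal or higher.

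A subject less than 1 year from the procedure at lock is censored at lock and is not carried to 1 year.

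**Step 2: worked case.** N = 100, 8 events by day 30, 6 later events, k event-free subjects last documented at day 30. The as-written SE is sqrt(0.14 × 0.86/100) = 3.47 points.

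| k | Rule | Rate | SE (points) | 95% CI |
|---|---|---|---|---|
| any | as written | 14/100 = 14.0% | 3.47 | 7.2 to 20.8 |
| 5 | last known status | 1 − 0.92 × 81/87 = 14.3% | 3.55 | 7.4 to 21.3 |
| 10 | last known status | 1 − 0.92 × 76/82 = 14.7% | 3.65 | 7.6 to 21.9 |

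Intervals are the estimate ± 1.96 Greenwood SE.

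**Step 3: expected size on the proxy curve.** The hazard is −ln(0.916)/(30/365) = 1.067 per year to day 30, then −ln(0.858/0.916)/(335/365) = 0.0713 per year. The expected as-written rate is (1 − L) × F(1 y) + L × E[F(time of loss)]. For loss uniform over the year, E[F] = 10.75%, so the shortfall is L × (14.2 − 10.75). If all loss or exit is at day 30, the shortfall is L × (14.2 − 8.4).

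| L | Shortfall, uniform | Shortfall, day 30 | Mean SE, uniform (as written vs last known) | Mean SE, day 30 (as written vs last known) |
|---|---|---|---|---|
| 5% | 0.17 | 0.29 | 3.44 vs 3.48 | 3.43 vs 3.50 |
| 10% | 0.35 | 0.58 | 3.42 vs 3.50 | 3.39 vs 3.54 |
| 20% | 0.69 | 1.16 | 3.38 vs 3.55 | 3.33 vs 3.64 |

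All entries are percentage points. SEs are means over 8,000 simulated cohorts of 100. For scale, the 95% half-width is 1.96 × sqrt(0.142 × 0.858/100) = 6.8 points.

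**Step 4: both sources together.** A separate simulation (4,000 cohorts of 100) with 5% leaving at day 30 and 10% lost uniformly gave 13.6% as written against 14.2%. An extreme case, with a 20% true rate, 5% leaving at day 30 and 30% lost, gave 17.6% against 20.0%. With no loss or exit the two rules agree.

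**The case against.** **Ordinary censoring is probably meant.** Carrying a lost subject to day 365 is imputation in effect, which SAP 2.8 rules out. The plan also uses a binomial proportion at 30 days but Kaplan-Meier at 1 year, a choice with little purpose if the latter collapses to events/N. This stands as evidence of intent, so a reader should not infer that the analysis will be done wrongly. It does not supply a date, and the one general sentence that does supply a date gives the wrong one.

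**The data are retrospective.** Subjects are found from "procedure records for potential study enrollment", and "data collection may also occur remotely by phone contact, mail, in-person, or through email". After a missed visit, Protocol 8.2 says: "The subject may therefore still return for subsequent follow-up visits and will not be withdrawn from the study". Many subjects may therefore be known alive beyond day 365. This stands and narrows the point to subjects with no later record. A reader might infer that everyone who leaves at 30 days without an implant must be incomplete at 1 year. The documents do not support that: only protocol data collection stops at 30 days, later records may exist, and nothing says that such a subject will be enrolled.

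**Bias against the truth is not proved.** The as-written rate is low relative to last-known-status censoring. Protocol 8.2 has sites try referring physicians and family before declaring loss, and deceased patients can be enrolled. If deaths are traced beyond the last visit while living subjects are censored at that visit, last-contact censoring can overstate the rate. This stands and shapes the fix.

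**The effect is small.** This also stands: the inputs are assumed, and no success decision depends on the result.

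**The 30-day endpoint.** A reader might extend the criticism to it. SAP 2.3.1.1 states that denominator openly, including subjects lost before the 30-day visit. A sensitivity analysis limited to subjects with an event or with follow-up to day 30 would keep early-lost subjects with events and drop those without, which biases the rate upward. No change is proposed there.

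**Conclusion.** The point holds as a defect in a written rule. It applies to subjects treated more than 1 year before lock whose event-free status is not documented to day 365. For them SAP 2.2.3, read literally, supplies event-free time that was not observed, and no other passage corrects it. Under assumed non-informative loss or exit of 5 to 20% and the 14.2% proxy rate, the understatement is about 0.2 to 1.2 points, with a slightly small standard error. It would be larger with heavier loss, a higher event rate, or higher risk among those who leave. In that last case, correct censoring would not remove all of it.

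The stronger conclusions, that the reported rate will certainly be wrong or that a claim of success is at risk, are not supported. The plan may well be carried out with ordinary censoring, and it contains no hypothesis test. The correction is still worth making because the sentence governs a co-primary estimate.

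**What to change.** Replace the sentence in SAP 2.2.3 with: *Subjects without an event are censored at the last date on which they are documented to be event-free, and no later than the endpoint timepoint or data lock.*

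- Apply the same ascertainment cut-off to events and to event-free status, so that deaths are not traced further than survival.
- Do not make study exit a censoring date in its own right. That would discard documented event-free status after day 30 in subjects without an implant.
- Leave the COVID-19 rule in SAP 2.3.1.2 unchanged.
- Report the number censored before 1 year by reason, with 30-day exits without an implant shown separately because their risk may differ. SAP 3.3 already summarises early-termination reasons by visit, so this only links that table to the Kaplan-Meier risk set.

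The cost is one sentence, a note on the cut-off and one table line, with no new data-collection timepoint. The 1-year rate may come out slightly higher and its interval slightly wider.

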#### 2.2.4 Analysis in Response to COVID-19 Impact

As the Coronavirus Disease 2019 (COVID-19) pandemic has spread around the globe, the following

analysis mechanism will be implemented to minimize the potential confounding effect from this emerging infectious disease for the trial primary endpoints set forth in assessing the trial success and labeling claims. In alignment with the EU guidance document "Guidance on the Management of Clinical Trials during the COVID-19 (Coronavirus) Pandemic" updated on 28-April-2020, and "FDA Guidance on Conduct of Clinical Trials of Medical Products during COVID-19 Public Health Emergency" updated on 03-June-2020, additional consideration was given to the impact of the COVID-19 pandemic on the primary endpoint analyses for this study. As such, prespecified methods are included in the sections that follow to indicate the handling of any outcomes impacted by COVID-19 as well as efforts to minimize missing endpoint data during the COVID-19 pandemic. Specific analyses to address COVID-19 impacts are included in relevant subsections in Section 2.3.

## 2.3 Endpoint Analysis

### 2.3.1 **Primary Endpoints**

#### 2.3.1.1 Primary Safety Endpoint

The primary safety composite endpoint is all-cause mortality, disabling stroke, life threatening bleeding requiring transfusion, AKI requiring dialysis, and major vascular complications at 30 days, as adjudicated by the CEC. COVID-19 relatedness of mortality, disabling stroke, life threatening bleeding requiring transfusion, AKI requiring dialysis, and major vascular complications will be adjudicated by the CEC, and any 30-day mortality, disabling stroke, life threatening bleeding requiring dialysis, and major vascular complications will be excluded from the primary analysis. The proportion of subjects experiencing a primary safety endpoint will be estimated from the binomial model. The 95% confidence intervals will be calculated using the exact Clopper-Pearson method.

The analysis population will include subjects enrolled in the study that is described in Section 2.1.1, including subjects who withdraw or are lost to follow-up prior to 30-day visit.

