## 12.2 Statistical Analyses

### 12.2.1 Primary Safety Endpoint Analyses

The primary safety composite endpoint is all-cause mortality, disabling stroke, life threatening bleeding requiring transfusion, AKI requiring dialysis, and major vascular complications at 30 days, as adjudicated by the CEC. The proportion of subjects experiencing a primary safety endpoint will be estimated from the binomial model. The 95% confidence intervals will be calculated using the exact Clopper–Pearson method.

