### 1.4 Endpoints

#### 1.4.1 **Primary Safety Endpoint**

Composite of all-cause mortality, disabling stroke, life threatening bleeding requiring transfusion, Acute Kidney Injury (AKI) requiring dialysis, and major vascular complications at 30 days.

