## 2.0 ANALYSIS CONSIDERATIONS

#### 2.1 Analysis Population

#### 2.1.1 **Primary Analysis Population**

The primary analysis population will include patients who have signed an Informed Consent Form (ICF), or for those patients deceased at the time of study screening, all local and national regulatory requirements were met for consent, and at minimum, the Portico delivery system entered his/her vasculature for an attempted Portico ViV implant. Subjects that are enrolled and later determined to be screen failures (those that do not meet all inclusion criteria or meet any exclusion criteria) will not be included in any analysis. Subjects that are enrolled in the Exploratory Arm of the study will not be included in the primary arm of the study.

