#### 2.3.1.2 **Primary Performance Endpoint**

The primary performance composite endpoint is all-cause mortality or disabling stroke at 1 year, adjudicated by the CEC. COVID-19 relatedness of mortality and disabling stroke will be adjudicated by the CEC, and any 1-year death or disabling stroke that is adjudicated as COVID-19 related will be excluded and subjects' follow-up will be censored at the first COVID-19 related event from the primary analysis. The proportion of subjects experiencing a primary performance endpoint will be estimated using the Kaplan-Meier (KM) method, and the standard error of KM estimate will be calculated with Greenwood method.

The analysis population will include subjects enrolled in the study that is described in Section 2.1.1.

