#### 2.12 Sensitivity Analysis

For the primary safety endpoint and performance endpoint, a sensitivity analysis will be conducted including all CEC adjudicated component events regardless of relationship to COVID-19 to assess the impact of the pandemic. Sensitivity analysis will also be conducted including all CEC adjudicated VARC-2 events and VARC-3 events regardless to COVID-19 to assess the impact of the pandemic.

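### The COVID-19 exclusion clause for the primary safety endpoint (SAP 2.3.1.1) omits its COVID-19 limit and merges two of the five components, so it misstates the intended rule

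*SAP*

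**What the plan says.** The primary safety endpoint has five components. Protocol 12.2.1 lists them as "all-cause mortality, disabling stroke, life threatening bleeding requiring transfusion, AKI requiring dialysis, and major vascular complications at 30 days", and SAP 1.4.1 agrees, with bleeding and kidney injury as separate items: "life threatening bleeding requiring transfusion, Acute Kidney Injury (AKI) requiring dialysis, and major vascular complications at 30 days".

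SAP 2.2.4 says that "prespecified methods are included in the sections that follow to indicate the handling of any outcomes impacted by COVID-19" and sends the reader to Section 2.3 for the specific analyses. In SAP 2.3.1.1 a single sentence does this for the safety endpoint. Its first half reads "COVID-19 relatedness of mortality, disabling stroke, life threatening bleeding requiring transfusion, AKI requiring dialysis, and major vascular complications will be adjudicated by the CEC". Its second half, the operative rule, reads "any 30-day mortality, disabling stroke, life threatening bleeding requiring dialysis, and major vascular complications will be excluded from the primary analysis".

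For the performance endpoint, SAP 2.3.1.2 says that "any 1-year death or disabling stroke that is adjudicated as COVID-19 related will be excluded", and adds that such subjects are censored at their first COVID-19-related event.

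Under SAP 2.12, "a sensitivity analysis will be conducted including all CEC adjudicated component events regardless of relationship to COVID-19". The safety rate is a binomial proportion with an exact Clopper-Pearson 95% interval, in the population of SAP 2.1.1.

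**The concern.** The second half of the sentence in SAP 2.3.1.1 does not follow from the first. It drops the COVID-19 condition, and it replaces two defined components with one that exists nowhere else in either document. As written, it contradicts the endpoint that the same paragraph has just defined.

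This matters because no other passage states the rule. Protocol 12.2.1 has no COVID-19 exclusion, SAP 2.2.4 defers to Section 2.3, and SAP 2.8 points back to 2.2.4 and the endpoint sections. Whoever programs this co-primary endpoint has only this clause to implement, and it has to be corrected by inference.

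The comparison in SAP 2.12 is also exposed. It is meant to show the effect of the pandemic as the difference between the all-event result and the primary result. If the primary result follows a wrong rule, that difference no longer measures what it should.

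**Working it through.** The plan gives no figure to reproduce here, so the check is a comparison of texts, followed by arithmetic on assumed counts.

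**Step 1: component by component.**

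| Component (SAP 1.4.1, Protocol 12.2.1) | CEC adjudicates COVID-19 relatedness (2.3.1.1, first half) | Named in the exclusion (2.3.1.1, second half) |
|---|---|---|
| Death from any cause | yes | yes |
| Disabling stroke | yes | yes |
| Life-threatening bleeding with transfusion | yes | no |
| AKI with dialysis | yes | no |
| Major vascular complication | yes | yes |
| Life-threatening bleeding with dialysis (not a component) | no | yes |

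Five components are defined and five are adjudicated. The exclusion has four items, and one of these is not a component.

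**Step 2: the limit.** The performance clause in 2.3.1.2 is restricted to events that the CEC attributes to COVID-19. The safety clause has no such restriction.

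**Step 3: what is meant.** Adjudicating relatedness serves no purpose unless the exclusion depends on it. SAP 2.2.4 concerns outcomes affected by COVID-19. SAP 2.12 brings events back irrespective of COVID-19, which is a meaningful contrast only if the primary analysis drops the COVID-19-related ones. All three point to the same rule: any of the five components, if COVID-19 related, is left out.

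**Step 4: how far the readings can differ.** N = 100 is the planned maximum (SAP 1.3). The 15 subjects with at least one component event are my assumption; the documents give no expected event rate and no COVID-19 rate. Intervals are exact Clopper-Pearson.

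*Literal reading, assuming no event is COVID-19 related.* The intended rate is 15/100 = 15.0% (8.65 to 23.53). The literal numerator is s, the number of the 15 who also have a dialysed AKI or a transfused bleed without dialysis. The error is (s − 15)/100.

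| s | Literal rate (95% CI) | Error, percentage points |
|---|---|---|
| 0 | 0.0% (0 to 3.62) | −15 |
| 7 | 7.0% (2.86 to 13.89) | −8 |
| 15 | 15.0% (8.65 to 23.53) | 0 |

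*Limit supplied from context, but the list followed as printed.* Let k of the 15 have as their only component event a COVID-19-related transfused bleed or dialysed AKI, and let no other event be COVID-19 related. The intended rate is (15 − k)/100, the reported rate is 15/100, and the error is k/100.

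| k | Intended rate (95% CI) | Reported rate | Error, percentage points |
|---|---|---|---|
| 0 | 15.0% (8.65 to 23.53) | 15.0% | 0 |
| 1 | 14.0% (7.87 to 22.37) | 15.0% | +1 |
| 3 | 12.0% (6.36 to 20.02) | 15.0% | +3 |

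**Step 5: event or subject.** The clause excludes from the analysis without saying whether the event or the subject is dropped. SAP 2.3.1.2 settles this by censoring, but a binomial endpoint has no censoring. SAP 2.1.1 keeps two groups out of the primary population: the exploratory arm, and those described as "Subjects that are enrolled and later determined to be screen failures". COVID-19 is not a ground for removal, and 2.3.1.1 says that the 2.1.1 population applies. That supports keeping the subject. The choice matters little: with k = 3, 12/100 = 12.0% if the subjects stay and 12/97 = 12.4% if they go.

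**The case against.** The strongest reply is that no competent reader would be misled. The literal reading defeats the endpoint, and the first half of the sentence supplies both the COVID-19 condition and the correct five components. The odd item looks like a copying slip from one use of the word requiring to the next. This largely stands: the intent is recoverable, and the design is sound.

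Two stronger inferences should be resisted. A reader might infer that the sponsor plans to strip all deaths, disabling strokes and major vascular complications from the primary result. SAP 2.2.4, 2.3.1.2 and 2.12 all speak against that. A reader might also infer that the probable outcome is a half-corrected rule, with the COVID-19 limit supplied but the list followed as printed. Nothing in the documents makes that likely, because the same half-sentence repairs both faults.

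It is also fair that an error would be visible. SAP 2.12 reports all adjudicated events, SAP 1.4.3 reports 30-day life-threatening bleeding and AKI by stage, SAP 3.2 summarises COVID-19-related adverse events, and under SAP 2.10 no hypothesis test is planned for the primary endpoints.

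What does not stand is that the clause can therefore be left alone. Those outputs would reveal a wrong primary estimate but would not correct it, and a prespecified primary rule should not need repair by inference. Text lost in conversion or redaction is an unlikely explanation: the sentence is grammatical and has no gap, unlike the missing counts in SAP 2.4 and 2.6, and wording is absent at two separate points.

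**Conclusion.** The point holds as a drafting error in the only operative COVID-19 rule for one of two co-primary endpoints. Followed as written, the clause contradicts the endpoint definition and leaves two components without an exclusion. It should be corrected before the primary analysis is programmed.

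The size is unknown. The percentages above rest on an assumed 15 event subjects in 100 and show only how the readings can diverge. If the intended rule is applied, the error is zero. It is also zero under the half-corrected reading if no COVID-19-related transfused bleed or dialysed AKI decides a subject's status.

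A reader might infer that the clause favours the device. The documents do not support a fixed direction: the literal reading would usually lower the rate, while the half-corrected one can only raise it.

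**What to change.** Replace the second half of the sentence in SAP 2.3.1.1 with wording to this effect:

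*A death, disabling stroke, life-threatening bleed requiring transfusion, acute kidney injury requiring dialysis, or major vascular complication within 30 days that the CEC adjudicates as COVID-19 related is not counted as a primary safety event. The subject stays in the Section 2.1.1 denominator and counts as an event only if another component event, not related to COVID-19, occurs within 30 days.*

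Keep the exact Clopper-Pearson interval and the SAP 2.12 sensitivity analysis as planned. The cost is one clause and an entry in the SAP revision history. No new data or analysis is needed, and neither the population nor the method changes.
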